### **5.3 Exclusion Criteria**

Patients meeting any of the following criteria are not eligible for participation in the study:

1. Pregnant or lactating women or planning to conceive a child during the next 3 months
2. Resting respiratory rate >20 breaths/min on room air or resting pulse rate  $\geq$  125 beats per minute
3. A rapidly worsening course that in the opinion of the Investigator or treating medical practitioner would lead to hospitalization within the next 24-48 hours
4. Any chronic pulmonary disease, including chronic obstructive pulmonary disease and asthma, or other respiratory diseases that could exacerbate independent of COVID-19
5. The following risk factors for severe COVID-19 (Cohorts 1 and 2 only) ([Centers for Disease Control 2020](#)):
  - a. Severe obesity, defined as body mass index  $\geq$  40 kg/m^2
  - b. History of
    - i. Severe cardiovascular disease, including but not limited to congestive heart failure, coronary artery disease, congenital heart disease, cardiomyopathies, or pulmonary hypertension
    - ii. Diabetes mellitus
    - iii. Chronic or current vaping or cigarette smoking
    - iv. Chronic kidney disease requiring dialysis
    - v. Chronic liver disease, including but not limited to chronic viral hepatitis, non-alcoholic steatohepatitis, or cirrhosis of any cause
    - vi. Hemoglobin disorder, including sickle cell disease and thalassemia

Based on ongoing review of efficacy and safety data, the DMC may remove part or all of these risk factors if preliminary data show no signal for adverse or paradoxical effects.

6. History of Bell's Palsy
-

[figure not shown]

7. Nasal conditions that might affect the suitability of intranasal medication, such as a history of chronic rhinitis, nasal septal defect, cleft palate, nasal polyps, or nasal surgery other than cosmetic rhinoplasty.
  8. Use of hydroxychloroquine within the past 4 months, chloroquine with the past 9 months, or other investigational agents for COVID-19 within the past 30 days
  9. History of conditions associated with immunocompromise, including but not limited to poorly controlled HIV, or treatments known to affect the immune system, including but not limited to oral or intravenous corticosteroids, alkylating drugs, antimetabolites, cytotoxic drugs, radiation, immune-modulating biologics (including IL-6, IL-12, Janus kinase inhibitors or antagonists), and cancer treatments, within 30 days of Screening or anticipated use within 6 months following participation in this study
  10. Any medical, psychiatric, or social condition or occupational or other responsibility that in the judgment of the Investigator would interfere with or serve as a contraindication to protocol adherence, assessment of safety (including reactogenicity), or a patient's ability to give informed consent
-

## **6 STUDY DRUG**

### **6.1 Description**

[figure not shown]
#### **6.1.1 *NasoVAX***

#### **6.1.2 *Placebo***

Commercially available 0.9% Sodium Chloride injectable solution for intranasal administration will be supplied to the site pharmacy. The placebo will be prepared in syringes identical to those used for the NasoVAX dose.

#### **6.1.3 *Packaging, Storage, and Handling***

Full preparation instructions are detailed in a separate pharmacy manual.

## **6.2 Randomization**

Following completion of the Screening activities, patients who meet all the inclusion and none of the exclusion criteria will be registered by the Interactive Web Response System (IWRS). Eligible patients will be randomly assigned in a 1:1 ratio to the NasoVAX or placebo group. Randomization will proceed in 3 cohorts defined by age and risk factors for severe COVID-19 ([Exclusion Criterion 5](#)) (Cohort 1, ages 18-49 years and risk factors disallowed; Cohort 2, ages 18 and above and risk factors disallowed; and Cohort 3, ages 18 and above and risk factors allowed) of approximately 20, 28, and 48 patients, respectively. The cohorts will be enrolled in ascending order, with Cohort 1 preceding Cohort 2, and Cohort 2 preceding Cohort 3. Cohort 2 will be stratified by age groups of 18-64 years and 65 years and above, whereas Cohort 3 will be stratified by age groups (ages 18-64 years, ages 65 and above) and co-morbidity (one or more risk factors present, no risk factors present). Patients in Cohorts 2 and 3 will be stratified first, and then randomized 1:1 to NasoVAX or placebo. Enrollment of patients ages 18-49 years will not exceed approximately 30% of the randomized population of either treatment arm. In addition, a minimum of 40% of Cohort 3 will either be 65 years or above or have one or more risk factors for severe COVID-19.

The randomization list will be generated by an independent unblinded statistician.

## **6.3 Dose and Administration**

NasoVAX or normal saline placebo will be administered as a single intranasal dose of 0.5 mL (0.25 mL in each nostril) on Day 1 in the supine position followed by remaining in supine position for 30 minutes, according to the patient's treatment assignment. Patients will be observed for at least 2 hours post intranasal administration.

## **6.4 Dosing Modifications**

As this is a single-dose study, no dose adjustments will be made on an individual patient basis.

## **6.5 Blinding and Unblinding**

The Pharmacy staff will be unblinded for the purpose of final drug preparation. The pharmacist will consult the unblinded study statistician for dose allocation and the Pharmacy staff will prepare each dose in compliance with the randomization list.

---

Due to the fact that formulations cannot be made to look identical, a blinded syringe will be used for administration. Study staff either preparing the syringes and/or administering the study drug will be independent and will not take part in any other activity of the study (eg, telephone contact).

Knowledge of the randomization list will be limited to the persons responsible for creation of the randomization list, pharmacy staff who prepare the study drugs, and any unblinded study monitors or auditors, until all data collection and verification activities and assignment of patients to the analysis populations has been completed, the database has been locked, and the study formally unblinded.

Data provided to the DMC may be unblinded, as required, for the assessment of safety.

If unblinding is required in the interest of the safety of a patient, an Investigator will discuss the matter with the Sponsor before unblinding. In a medical emergency, the Investigator or delegate may unblind via the IWRS for that patient without prior consultation with the Sponsor. In that event, the Investigator or delegate will notify the Sponsor as soon as possible that the randomization code has been broken for the patient. If the blind is broken, the date, time, and reason must be recorded.

Patients may also be unblinded for the assessment of Stopping Rules, DMC evaluations, expedited safety reports, and the emergency unblinding of individual patients, as detailed in a separate Safety Management Plan.

## **6.6 Accountability**

The Investigator (or designee) will maintain an accurate record of the receipt of each IP as shipped by the Sponsor (or designee), including the date received. In addition, an accurate IP disposition record will be kept, specifying the amount dispensed for each patient and the dates of dispensation and any returns.

Sponsor approval is required for on-site destruction of all used IP and shipment of all unused IP back to the Sponsor at the completion of the study once all reconciliation has occurred.

## **6.7 Prior and Concomitant Therapy**

In the interests of patient safety and acceptable standards of medical care, both the Investigator and patient personal physician(s) will be permitted to prescribe additional treatment(s) at his/her discretion.

Any medications that are ongoing at Screening are to be documented in the electronic case report form (eCRF). Thereafter, all concomitant medications, including supplemental oxygen, through 30 days after study drug administration are to be documented in the eCRF.

Concomitant medications, including supplemental oxygen, are to be recorded in the source documents and in the eCRF.

---

### **6.7.1 Prohibited Prior and Concomitant Medications**

Prohibited prior and concomitant medications are as follows:

- Hydroxychloroquine within 4 months or chloroquine within 9 months of Screening
- Any treatment known to affect the immune system, including but not limited to oral or intravenous corticosteroids, alkylating drugs, antimetabolites, cytotoxic drugs, radiation, immune-modulating biologics, within 30 days of Screening
- Live vaccines (such as live influenza vaccinations or live travel vaccinations) within 30 days of Screening and through Day 14 post study drug administration
- Receipt of any investigational drug or treatment within 30 days of Screening.

The above medications are prohibited through Day 14 or hospitalization, and all other concomitant medications are permitted. If a patient is hospitalized due to COVID-19, there are no restrictions regarding concomitant medications. However, all medications administered, including antipyretics, bronchodilators, and supplemental oxygen requirements, are to be documented in the eCRF.

### **6.8 Contraception**

All female patients of childbearing potential must practice a highly effective method of contraception for 28 days after study drug administration. Male patients with partners of childbearing potential must practice a highly effective method of contraception for 45 days after study drug administration.

Highly effective methods of contraception include, but are not limited to, abstinence, sex only with persons of the same sex, monogamous relationship with a postmenopausal partner, monogamous relationship with vasectomized partner, vasectomy, licensed hormonal methods, intrauterine device, or consistent use of a barrier method (eg, condom, diaphragm) with spermicide.

### **6.9 Compliance**

A single dose of study drug will be administered by study personnel and therefore compliance with study drug dosing is not a concern. The study personnel will be appropriately trained on study drug administration procedures and documentation requirements prior to study start.

Non-compliance with study procedures will be reported to the Sponsor who will decide if persistent non-compliant patients should be withdrawn from continued study participation.

---

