## **7 PREMATURE DISCONTINUATION**

### **7.1 Individual Patients**

Patients can choose to discontinue study participation at any time, for any reason, without prejudice to their future medical care. Patients could be discontinued for any of the following reasons:

- Patient request/withdrawal of consent
- Noncompliance with study requirements
- Loss to follow-up
- Investigator discretion
- Sponsor request, including termination of the study by the Sponsor

For all patients who discontinue for reasons other than withdrawal of consent, a final telephone contact will be made by study center personnel to document final outcome and AEs. Serious adverse event (SAEs), hospital, and ICU lengths of stays, and mortality in hospitalized patients also will be documented.

Eligible patients who are randomized and withdrawn before study drug administration will be replaced. Patients who receive study drug who are subsequently withdrawn from the study will not be replaced.

To optimize the safety of study participants, once patients receive study drug, all efforts will be made to monitor their clinical courses according to study procedures.

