#### **8.4 Concomitant Care and Unscheduled Visits**

No study center visits are scheduled other than Screening. Patients will continue to follow with their personal doctors during the study and receive medications at their direction after Screening. The prescription and use of any prohibited medications through Day 14 will be recorded but will not result in the discontinuation of any study procedures. If it is determined that the patient is in the need of an unscheduled clinic visit for further evaluation, an unscheduled visit with the personal doctor, or hospitalization, these arrangements will be made. The Investigator will assist in making these arrangements whenever possible. The decision to seek this unscheduled care will be at the discretion of the patient, the personal doctor, or Investigator.

---

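### Dosed patients can be withdrawn for missed procedures with only one undated final call required, so later hospitalizations and deaths can go unrecorded

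*Protocol*

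**What the plan says.** Protocol 6.9 first observes: "A single dose of study drug will be administered by study personnel and therefore compliance with study drug dosing is not a concern". It then adds: "Non-compliance with study procedures will be reported to the Sponsor who will decide if persistent non-compliant patients should be withdrawn from continued study participation". It does not define persistent.

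Protocol 7.1 lists "Noncompliance with study requirements" among the reasons for discontinuing a patient, alongside investigator discretion and sponsor request. For everyone who leaves for a reason other than withdrawn consent, "a final telephone contact will be made by study center personnel to document final outcome and AEs". No day is given for that contact. The section continues: "Serious adverse event (SAEs), hospital, and ICU lengths of stays, and mortality in hospitalized patients also will be documented". No time window is attached to this either. On replacement it says: "Patients who receive study drug who are subsequently withdrawn from the study will not be replaced". It closes with a commitment that, for safety, "once patients receive study drug, all efforts will be made to monitor their clinical courses according to study procedures". SAP 5.1.1 repeats the section.

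The outcomes affected are defined in Protocol 3.1 and 3.2. Hospitalization is one of the two ways to meet the primary endpoint. Hospitalization by level of oxygen support and all-cause mortality, both through Day 42, are secondary endpoints.

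**The concern.** In most trials, discontinuation separates stopping treatment from stopping follow-up. Here the whole treatment is given on Day 1, so withdrawal for non-compliance can only mean that observation ends. The procedures a patient can fail to comply with are the home readings, the diary and the calls, and a patient may stop these because he or she is getting worse. The rule may therefore remove from view some of the patients most likely to have the primary event.

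Two uses of the data are at stake. One is the primary proportion and the Day 42 secondary endpoints. The other is safety oversight: the hospitalization halt limits in Protocol 7.2 and the DMC review between cohorts both depend on complete counts of admissions. In addition, Protocol 4.1 pauses enrollment until every patient in a cohort has finished 14 days of home assessments or been hospitalized. A patient withdrawn early and not admitted literally meets neither condition.

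**Working it through.** **The rules side by side.** A patient who stays in the study is called daily from Day 2 to Day 14 and again at Days 21 and 28, and is followed to Day 42 if still hospitalized. If calls are not completed, Protocol 8.2.3 provides for contacting family or caregivers. A patient withdrawn under 6.9 or 7.1 has one required contact of unstated date. Nothing requires the site to ask about admission or vital status after it.

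**What the SAP does with the gap.** SAP 9.9 and 9.9.6 analyze observed data only. The optional imputation in 9.9.6 covers data missing because of death or hospitalization, not withdrawal. SAP 9.9.3 assumes non-informative censoring, which is doubtful if non-compliance is related to worsening. SAP 9.9.1 does not say how an mITT patient who stops measurements without a recorded event is classified in the primary proportion.

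**Size.** The documents give no event rate, withdrawal rate or power, so there is no figure of the plan's own to reproduce. The following is an illustration.

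- Arm sizes (Protocol 4.1): 10 + 14 + 24 = 48.
- Hospitalization rates, assumed equal to the halt ceilings in Protocol 7.2 (15%, 20%, 25%). These are ceilings, not expected rates: 10 × 0.15 + 14 × 0.20 + 24 × 0.25 = 1.5 + 2.8 + 6.0 = 10.3 per arm, or 10.3/48 = 21.5%.
- Share withdrawn (assumed): 5% to 20%.
- Share of their admissions that follow the final call and go unrecorded (assumed): 25% to 100%.

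Unrecorded admissions per arm = 10.3 × share withdrawn × share after the call.

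| Withdrawn | 25% after call | 50% | 100% |
|---|---|---|---|
| 5% | 0.13 | 0.26 | 0.52 |
| 10% | 0.26 | 0.52 | 1.03 |
| 20% | 0.52 | 1.03 | 2.06 |

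If such patients were counted as not worsened, the recorded hospitalization rate would fall from 21.5% to between 21.2% and 17.2%. Each lost admission is 1/48 = 2.1 percentage points of an arm.

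The table gives withdrawn patients the average risk. Doubling their risk doubles each cell. With half of the admissions missed, that is 0.5 to 2.1 per arm; only the extreme corner (20% withdrawn, all missed) goes higher, to 2 × 2.06 = 4.1.

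**Power.** With equal loss in both arms, half of the withdrawn patients' events missed and 5-20% withdrawn, power at one-sided 0.025 for an assumed 21.5% versus 10.75% falls from 29.7% to between 28.9% and 26.8%. The effect is small.

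**Halt limits**, using the planned arm sizes as denominators:

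- Cohort 1: 1/10 = 10% does not exceed 15%; 2/10 = 20% does.
- Cohort 2: 2/14 = 14.3% does not exceed 20%; 3/14 = 21.4% does.
- Cohort 3: 6/24 = 25.0% does not exceed 25%; 7/24 = 29.2% does.

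In each cohort a single unrecorded admission can decide whether the limit is crossed.

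**The case against.** The best defense is that Protocol 7.1 points toward continued follow-up. Its sentence specific to dosed patients commits to all efforts to monitor them, and it names SAEs and hospital and ICU stays as data to be documented after discontinuation. The final contact is meant to establish the patient's outcome and is undated, so it could be an end-of-study call. Withdrawal also needs persistent non-compliance and a sponsor decision. Sections 7.2 and 9.7 promise the DMC real-time notice of admissions and deaths without excluding withdrawn patients. All of this stands, and it is why events can be lost rather than will be lost. It does not close the gap: a site that calls on the day of withdrawal and then stops has done everything that 7.1 specifically requires, and the DMC can be told only what the site learns.

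Three stronger readings are tempting and not supported.

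- A reader might infer that a withdrawn patient is counted as not worsened. The SAP is silent on this.
- A reader might infer a contradiction with Protocol 8.4, under which use of a prohibited drug "will be recorded but will not result in the discontinuation of any study procedures". That section concerns a different trigger. It shows only that the protocol elsewhere separates a departure from the end of follow-up.
- A reader might infer bias between arms. If one arm alone had 10-20% withdrawn with 50-100% of their events missed, equal true rates of 21.5% would differ by 1.1 to 4.3 percentage points. The double-blind design and restricted access to the randomization list make such an imbalance less likely, and nothing in the documents indicates one.

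**Conclusion.** The concern holds in a limited form. A stated rule lets dosed patients leave follow-up for reasons that may be related to their illness, with no dated or continuing check on hospitalization or death. It sits uneasily with the monitoring commitment in the same part of the protocol. The likely loss is about 0.1 to 2 hospitalizations per arm, which rests entirely on the assumed withdrawal share, the assumed timing of the call, and halt ceilings used as event rates at average risk. In an exploratory study not sized on power, the effect on the primary comparison is modest. The clearer reason to act is that the halt limits turn on single patients and the loss is cheap to avoid. This is a recommended improvement, not a flaw that invalidates the design.

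**What to change.** Reconcile Protocol 6.9 and 7.1 and SAP 5.1.1 as follows.

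- State that, after dosing, non-compliance or investigator or sponsor discretion ends only the home measurements and diary.
- Unless consent to follow-up is withdrawn, collect hospitalization and vital status from the patient or named caregiver at Day 14 and at the scheduled Day 21 and 28 calls, and through Day 42 if hospitalized. Add a Day 42 vital-status check if the Day 42 mortality endpoint is kept for all patients.
- Replace the clause that limits mortality to hospitalized patients with one covering hospitalization and vital status in all discontinued patients.
- In Protocol 4.1, let the Day 14 status contact satisfy the cohort-pause condition for patients who have stopped home measurements.
- In the SAP, state how mITT patients who stop measurements without a recorded event are classified in the primary proportion, and add a sensitivity analysis that counts them as worsened.

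The cost is wording in two documents and a few calls for a small number of patients. Most of these calls are already scheduled, and caregiver contacts are already collected at Screening (Protocol 8.1.1). The downside is site effort spent on patients who may not answer.

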## **7 PREMATURE DISCONTINUATION**

### **7.1 Individual Patients**

Patients can choose to discontinue study participation at any time, for any reason, without prejudice to their future medical care. Patients could be discontinued for any of the following reasons:

- Patient request/withdrawal of consent
- Noncompliance with study requirements
- Loss to follow-up
- Investigator discretion
- Sponsor request, including termination of the study by the Sponsor

For all patients who discontinue for reasons other than withdrawal of consent, a final telephone contact will be made by study center personnel to document final outcome and AEs. Serious adverse event (SAEs), hospital, and ICU lengths of stays, and mortality in hospitalized patients also will be documented.

Eligible patients who are randomized and withdrawn before study drug administration will be replaced. Patients who receive study drug who are subsequently withdrawn from the study will not be replaced.

To optimize the safety of study participants, once patients receive study drug, all efforts will be made to monitor their clinical courses according to study procedures.

### **7.2 Stopping Rules**

Enrollment and study drug treatment will be temporarily halted pending DMC review for any of the following reasons:

- Any SAE considered possibly or probably related to study drug
  - Any Grade 4 or Grade 5 (death) AE considered possibly or probably related to study drug
  - Three or more subjects in the same cohort experience the same Grade 3 AE in the same Medical Dictionary for Regulatory Activities (MedDRA) System Organ Class considered possibly or probably related to study drug
-

- Hospitalization rates in either treatment group in individual cohorts exceeding:
  - 15% (Cohort 1 only)
  - 20% (Cohort 2 only)
  - 25% (Cohort 3 only)
- Mechanical ventilation rates in either treatment group in individual cohorts equal to or exceeding:
  - 2 patients (Cohort 1 only)
  - 3 patients (Cohort 2 only)
  - 4 patients (Cohort 3 only)

The DMC will be advised each time a patient dies or is hospitalized. The DMC may unblind individual patients for the assessment of the relationship of the event to study drug. The DMC may recommend resumption of dosing if subject safety is not considered to be at significant risk following analysis.

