**Stopping Rules:**

Enrollment and study drug treatment will be temporarily halted pending DMC review for any of the following reasons:

- a. Any serious adverse event (SAE) considered possibly or probably related to study drug
- b. Any Grade 4 or Grade 5 (death) AE considered possibly or probably related to study drug
- c. Three or more subjects in the same cohort experience the same Grade 3 AE in the same Medical Dictionary for Regulatory Activities (MedDRA) System Organ Class considered possibly or probably related to study drug
- d. Hospitalization rates in either treatment group in individual cohorts exceeding:
  - 15% (Cohort 1 only)
  - 20% (Cohort 2 only)
  - 25% (Cohort 3 only)
- e. Mechanical ventilation rates in either treatment group in individual cohorts equal to or exceeding:
  - 2 patients (Cohort 1 only)
  - 3 patients (Cohort 2 only)
  - 4 patients (Cohort 3 only)

The DMC will be advised each time a patient dies or is hospitalized. The DMC may unblind individual patients for the assessment of the relationship of the event to study drug. The DMC may recommend resumption of dosing if subject safety is not considered to be at significant risk following analysis.

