### **8.2.6 Vital Status**

Vital status is to be documented at each study contact. If the patient died due to a reason other than COVID-19, the primary cause of death is to be recorded and reported as an SAE. Death due to worsening fever, cough, shortness of breath, resting SpO2, or resting pulse rate or COVID-19 symptoms that are reported at Screening ([Section 8.1.2](#)) is not considered to be an SAE in the context of this study although cause of death will be reviewed by the DMC in real time.

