## **9 ADVERSE EVENTS**

### **9.1 Definitions**

#### **9.1.1 *Adverse Event***

An AE is defined as any untoward medical occurrence associated with the use of a drug in humans, whether or not considered drug related. An AE can therefore be any unfavorable and unintended sign (including an abnormal laboratory finding), symptom, or disease temporally associated with the use of the investigational product whether or not related to the investigational product. An AE can be any sign, symptom, or diagnosis that appears or changes in intensity during the course of the study.

Unchanged chronic conditions are not AEs and should not be recorded on the AE pages of the eCRF. These medical conditions should be adequately documented on the appropriate page of the eCRF (medical history or physical examination). However, medical conditions present on the first day of treatment that worsen in intensity or frequency during the treatment or post-treatment periods in a manner not consistent with natural disease progression should be reported and recorded as AEs. The Investigator will actively solicit this information and assess the event in terms of severity and relationship to the study treatment regimen.

The objective of this study is to assess the effective and safety of NasoVAX in preventing clinical worsening of early COVID-19. The worsening of fever, cough, shortness of breath, resting SpO2 or resting pulse rate and symptoms of COVID-19 that are reported in the eDiary during Screening ([Section 8.1.2](#)) will be captured in aggregate in the eCRF and will not be reported as AEs.

The term AE is used to include any AE whether serious or not serious.

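### The hospitalization halting rule does not count death, so a COVID-19 death in a patient never admitted and not judged drug-related enters no halting count

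*Protocol*

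**What the plan says.** The synopsis letters the five halting rules (a) to (e). Protocol 7.2 and SAP 5.1.2 give the same rules as bullets.

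- Rules (a), (b) and (c) each require an event judged possibly or probably related. Death is named only in (b): "Any Grade 4 or Grade 5 (death) AE considered possibly or probably related to study drug".
- Rule (d) needs no causality judgment: "Hospitalization rates in either treatment group in individual cohorts exceeding" 15%, 20% and 25% in Cohorts 1, 2 and 3.
- Rule (e) needs none either: "Mechanical ventilation rates in either treatment group in individual cohorts equal to or exceeding" 2, 3 and 4 patients.

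Section 7.2 then adds: "The DMC will be advised each time a patient dies or is hospitalized". It also says: "The DMC may unblind individual patients for the assessment of the relationship of the event to study drug".

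Three other sections decide what can reach rules (a) and (b). Under 8.2.6, death from worsening of the COVID-19 symptoms reported at Screening "is not considered to be an SAE in the context of this study although cause of death will be reviewed by the DMC"; 9.6.3 repeats this for both admissions and deaths. Under 9.1.1, worsening of those symptoms "will be captured in aggregate in the eCRF and will not be reported as AEs". Under 9.3.2, an event can be called possibly related only if concurrent disease is an improbable explanation.

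**The concern.** Every participant has COVID-19, so a death from COVID-19 will seldom meet the definition of possibly related, and 8.2.6 and 9.1.1 generally remove it from the SAEs and AEs on which relatedness is judged. If the patient was also never admitted or ventilated (a home death, for short), rules (d) and (e) do not see it either.

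The result is an uneven scheme. The DMC is told of every admission as well as every death, yet the sponsor still set a numerical limit for admissions that stops dosing without waiting for a judgment. Nothing in the documents explains why the worse outcome has no such limit. At stake is whether further patients in the same cohort may be dosed while the DMC examines a death that, added to the admissions already seen, would bring the arm past its limit.

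**Working it through.** **Inputs.** Arm sizes of about 10, 14 and 24 (Protocol 4.1; SAP Table 1). Limits for (d) and (e) from Protocol 7.2. The plan gives no operating characteristics for these rules, so there is no stated figure to reproduce.

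**Step 1: where a home death not judged related is counted.**

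| Rule | Counts | Needs relatedness? | Contribution of the home death |
|---|---|---|---|
| (a) | SAE | yes | 0 |
| (b) | Grade 4 or 5 AE | yes | 0 |
| (c) | same Grade 3 AE, three or more subjects | yes | 0 |
| (d) | hospitalization | no | 0 |
| (e) | mechanical ventilation | no | 0 |

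**Step 2: where (d) halts in a full arm.** The largest count that does not exceed the limit is floor(n × limit).

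- Cohort 1: 10 × 0.15 = 1.5, so 1 is tolerated and 2 halts.
- Cohort 2: 14 × 0.20 = 2.8, so 2 are tolerated and 3 halt.
- Cohort 3: 24 × 0.25 = 6, so 6 are tolerated and 7 halt.

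**Step 3: what one home death changes if (d) counts it.**

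| Full arm | Count now | Count with death included | Limit |
|---|---|---|---|
| Cohort 1: 1 admission + 1 home death | 1/10 = 10.0%, no halt | 2/10 = 20.0%, halt | 15% |
| Cohort 2: 2 admissions + 1 home death | 2/14 = 14.3%, no halt | 3/14 = 21.4%, halt | 20% |
| Cohort 3: 6 admissions + 1 home death | 6/24 = 25.0%, no halt | 7/24 = 29.2%, halt | 25% |

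The Cohort 3 row supposes fewer than four ventilated patients; otherwise (e) has already halted the arm.

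**Step 4: the other reading of the denominator.** The protocol does not say whether (d) divides by the full arm or by those dosed so far. On a running denominator one event halts while the arm is small:

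- Cohort 1: 1/6 = 16.7% halts, 1/7 = 14.3% does not.
- Cohort 2: 1/4 = 25.0% halts, 1/5 = 20.0% does not.
- Cohort 3: 1/3 = 33.3% halts, 1/4 = 25.0% does not.

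A single home death would then pause dosing with up to 6, 4 or 3 patients dosed in that arm, exactly as a single admission does now.

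**Step 5: added chance of a pause, full arm.** Let each patient be admitted with probability p or die at home with probability h. Admissions A and home deaths H are multinomial, and ventilations V given A are Bin(A, 0.30). The arm halts now if A ≥ r or V ≥ v, and after the change if A + H ≥ r or V ≥ v, with r = 2, 3, 7 and v = 2, 3, 4. In Cohorts 1 and 2, r = v and V cannot exceed A, so only (d) matters there. The documents give no p, h or ventilated share. I assumed p from 2% to 25%, h from 0.1% to 1%, and 30% of admissions ventilated.

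Example, Cohort 1, p = 10%, h = 1%:

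- Now: 1 − 0.90^10 − 10 × 0.10 × 0.90^9 = 26.4%.
- Changed: 1 − 0.89^10 − 10 × 0.11 × 0.89^9 = 30.3%.
- Added: 3.9 points.

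Ranges over the assumed values:

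- Cohort 1: 0.2 to 3.9 points.
- Cohort 2: 0.04 to 4.1 points (maximum at p = 15%, h = 1%).
- Cohort 3: 0 to 4.2 points (maximum at p = 25%, h = 1%).

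**Step 6: would adding death to (e) as well be justified?** In Cohorts 1 and 2 it changes nothing once (d) counts death, because both rules then halt at 2 and 3. In Cohort 3, suppose also that 25% of admissions end in death without ventilation. Changing both rules then adds 3.1 points at p = 10% and 11.9 at p = 25% even when h = 0, and up to 17.5 points (p = 20%) when h = 1%. Changing (d) alone adds 0 when h = 0.

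**The case against.** The best defense is that a halt only pauses dosing pending DMC review, and for death that review already begins with the first case. The DMC is notified, examines the cause in real time whether or not the death is an SAE, may unblind, can decide on continuation over any safety concern (4.2), and must review each cohort before the next opens (4.1). Home deaths should also be rare: entry requires resting SpO2 of at least 96.0% twice and excludes a rapidly worsening course, patients are called daily through Day 14, and the investigator helps arrange admission (8.4). All of this stands and makes the gap narrow. It does not close it, because notification does not itself stop dosing, and the same notification was not treated as sufficient for admissions.

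A reader might infer more than the documents support:

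- *That deaths go unmonitored.* They do not; only the automatic pause is absent.
- *That no death can halt the trial.* A related death does, under (b). Section 8.2.6 also keeps other causes in the SAE system ("If the patient died due to a reason other than COVID-19, the primary cause of death is to be recorded" and reported as an SAE), so those halt under (a) if related. Even a COVID-19 death has a narrow route: 9.1.1 treats worsening that departs from the natural course of a condition as an AE.
- *That deaths in hospital are missed.* The admission has already counted in (d).
- *That the ventilation rule should count death too.* Step 6 shows this is redundant in Cohorts 1 and 2. In Cohort 3 it would mainly count in-hospital deaths against a limit set for ventilation alone.
- *That no death trigger exists anywhere.* The DMC charter (9.7) and the Safety Management Plan (6.5) are not among the documents.

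**Conclusion.** The point holds in a limited form and is worth considering rather than essential. On the wording of 7.2, the synopsis and SAP 5.1.2, a COVID-19 death without admission or ventilation, not judged related, contributes zero to every halting rule in every cohort. That part rests on the text alone. The consequence is a missing automatic pause within a cohort, not missing oversight. It bites when admissions in an arm are just below the limit: at 1 of 10, 2 of 14 or 6 of 24 in full arms.

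The price of closing the gap, at most about 4 percentage points of added pause probability per full arm, rests on the assumed risks in Step 5 and on a full-arm denominator. Confidence is medium, because the two documents not seen could already supply the trigger.

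**What to change.** In Protocol 7.2, the synopsis copy and SAP 5.1.2, change the numerator of the hospitalization rule to *hospitalization or death from any cause, each patient counted once*. Keep the limits of 15%, 20% and 25% and the existing DMC process. Counting any cause matches the rule as it stands, which has no causality condition. Add one sentence saying that the AE and SAE exclusions in 8.2.6, 9.1.1 and 9.6.3 do not govern this count. Leave the ventilation rule unchanged. The SAP copy has to change too, because SAP 9.13 lets the SAP prevail in a conflict. If the charter or Safety Management Plan already holds a death trigger, cite it in 7.2 instead.

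Cost: a protocol amendment with written IRB approval and regulatory submission (12.5), across up to 12 centers. No new data are needed, since the DMC already receives every death. The trade-off is an occasional earlier temporary pause, including for an unrelated death or one on placebo, after which the DMC may recommend that dosing resume.
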